FLUS can diagnose COVID-19 pneumonia with high sensitivity and specificity using PCR-test and chest radiograph as reference.

Aim

To study the ability of FLUS in COVID-19 to predictive respiratory failure.

To study the diagnostic capability of FLUS to find COVID-19 pneumonia.

To study risk-stratifying capability of FLUS in patients with COVID-19 symptoms.

Method

Design

Multicenter prospective cohort study with convenience sampling.

Setting

Emergency departments or internal medicine departments who admit patients with COVID-19 symptoms.

Participants

Patients who have COVID-19 symptoms and require diagnostic testing.

Patients who have a positive SAR-CoV-2 PCR-test and require admission to hospital.

Inclusion criteria

- Patients who are seen in COVID-clinics or emergency departments due to symptoms that require diagnostic work-up to COVID-19.
- Patients admitted to hospital with positive SARS-COV-2 PCR-test and in whom FLUS is performed less than 48 hours after admission.

Exclusion criteria

- Age less than 18 year.
- Former participation in this study.
- Pre-FLUS ventilator support.

Double inclusion

Inclusion in this study will not restrict patient from inclusion in other studies.

Recruitment

Participants are recruited at the local hospital. In Denmark the study is labelled quality assurance and the need for informed consent is thus waived. Local regulations are followed and it is the responsibility of each inclusion site to achieve appropriate regulatory permissions including need for approval from local ethical committees and healthcare authorities.

Variables

Ultrasound variables: FLUS are performed according to ERS guidelines and to Standard of Operating Procedure specific to this study. Film clips are recorded and saved for later evaluation. 14 zones are scanned. Film clips are marked with scanning position (L1, L2...etc.). If the patient is unable to sit, only anterior and lateral zones are scanned. FLUS findings are assessed on the film clips by an observer blinded to other variables. Findings are coded with 1/0 for presence of pneumonia. Moreover, a scoring system is applied:

FLUS findings	Score
Normal FLUS	0
Interstitial syndrome, defined as more than 3 B-lines in a single zone.	1
Diverse B-lines or irregular pleura	
Interstitial syndrome, defined as more than 3 B-lines in a single zone.	2
Confluent B-lines.	
Consolidations (sub-pleurale, lobar, with or without air-bronchograms)	3

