Data on FLUS operator: Level of medical degree. Years of experience with lung ultrasound. Completed training in FLUS.

From patient files the following data is extracted:

Patient demographic: Sex, age, height, weight, co-morbidities.

Clinical data on time of admission: Blood pressure, pulse, peripheral saturation, respiratory frequency, temperature, length of illness, list of symptoms, limitation to treatment i.e. not suited or willing to intensive care treatment and intubation.

Data from radiographic diagnostics: Result of chest radiograph, CT or HRCT scanning, if done for clinical reasons. No further review of radiographic examinations is performed. Results given by local radiology department is used.

Microbiological data: Result of SARS-CoV-2 PCR-test from nasal/oral/laryngeal or tracheal samples.

Data from admission: Time of admission. Place of admission. Time of dismissal. Admission to intensive care. Intubation. Time in ventilator. Death, survival. In hospital survival, 14- and 30-days survival.

Endpoints

Primary endpoint: FLUS (binary: positive/negative pneumonia) related to intubation (yes/no).

Secondary endpoints: Relationship between FLUS and SARS-CoV-2 PCR result.

Relationship between FLUS and radiographic findings.

Relationship between FLUS and admission to intensive care (not intubation).

Relationship between FLUS and re-admission (Patient returning to emergency department or COVID-clinic).

Scores of FLUS findings in different zones.

Data management

The study uses convenience sampling as FLUS may not be available at all times. FLUS is performed by the clinician such that only doctors with clinically relevant work are allowed to scan the patient. This minimizes the risk of disease transfer to doctors and reduces the use of protection equipment.

Ultrasound film clips are recorded according to standard operating procedure. Film clips are stored securely, according to local legal regulations. All variables extracted from patient files are stored in an eCRF using REDCap supplied by Aarhus University Hospital.

Every site will have access to enter data in data capture instruments. Access to REDCap is managed by the project steering committee at Aarhus University Hospital.

Data analysis

All data are analyzed in Stata.

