Binary endpoints, including primary endpoint, are analyzed using Chi-2 test. Continuous data are assessed for parametric distribution and analyzed with Student's T-test on logarithmic transformed data in case of non-parametric distribution.

Level of statistical significance is set to 5%.

A logistic prediction model will be developed. Dependent variable is intubation. Independent variables are age (continuous), FLUS result (Binary or ordinal), SARS-CoV-2 status (Binary) and peripheral oxygen saturation (continuous).

The data set will be divided in two. One is used for model development and one is used for validation of the model. Geographic external validity is tested. Internal validity is tested with bootstrapping method. Sensitivity, specificity and ROC AUC is calculated.

Sample size

No prior publications are available for sample size estimation.

For the prediction model we wish to include 10-15 events per independent variable, 50-75 events. From early estimations about 20% of admitted patients requiring intubation our estimate is 375-400 participants.

Inclusion period

An end date is set to May 15 2020. If COVID-19 pandemic is ongoing at this time point the study may extent.

Blinding

Ultrasound film clips are analyzed blinded to other variables.

Plan for publication

Data analysis is estimated to end July 1. 2020. Article submission is estimated to October, 2020.

Preliminary data analysis

Available data will be analyzed soon after 15. May.

Ethical considerations

FLUS is without any risk to patients. COVID-19 is an infectious disease and isolation is needed. Contamination during the study needs to be avoided. For this reason, FLUS is only performed by the physicians who are required to see the patient regardless of this study. The ultrasound equipment is cleaned after each examination in accordance with local guidelines.

Legal regulations

In Denmark the study is classified as a quality assurance project. Arrangements and permission to access to patient files in each site is required. According to guidance from the legal office at Region Midt a data management agreement is not needed.

International data agreements are required to data transfer from international sites to Denmark.

All international sites must adhere to local regulation. Responsibility of this is on the international site.

Publication

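### The FLUS–PCR endpoint has no stated population; pooling inpatients enrolled as PCR-positive mixes an admitted-versus-work-up difference into the association and can inflate sensitivity

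*Protocol*

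**What the plan says.** The Protocol (Hypothesis) states a diagnostic claim: "FLUS can diagnose COVID-19 pneumonia with high sensitivity and specificity using PCR-test and chest radiograph as reference". Under Endpoints, a secondary endpoint is "Relationship between FLUS and SARS-CoV-2 PCR result". Under Data analysis, "Binary endpoints, including primary endpoint, are analyzed using Chi-2 test", at a 5% significance level.

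Inclusion criteria open two routes into the cohort:

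- Work-up route: "Patients who are seen in COVID-clinics or emergency departments due to symptoms that require diagnostic work-up to COVID-19". PCR may turn out positive or negative.
- Positive-PCR route: "Patients admitted to hospital with positive SARS-COV-2 PCR-test and in whom FLUS is performed less than 48 hours after admission". PCR is positive by definition.

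There is no matching route for PCR-negative inpatients. Neither Endpoints nor Data analysis limits the FLUS–PCR comparison to one route, stratifies it or adjusts it. The SAP lists the PCR result only as a descriptive yes/no item and specifies no FLUS–PCR test, so it does not settle the population.

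**The concern.** The second route selects patients on the reference result itself. All of its patients fall in the PCR-positive row of the FLUS-by-PCR table, while every PCR-negative patient comes from the work-up route. A whole-cohort test thus compares work-up PCR-negatives with a blend of work-up PCR-positives and PCR-positive inpatients. If inpatients have abnormal FLUS more often, that difference feeds into the association, and sensitivity against PCR rises with it.

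The Protocol's Background makes such a difference plausible. It reports abnormal chest radiographs in more than 80% of patients admitted with COVID-19, and it expects symptomatic patients without pneumonic FLUS findings to be manageable outside hospital.

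The risk is that a significant result, or a high apparent sensitivity, is read as support for the diagnostic hypothesis when part of it reflects who was admitted. Blinded reading of the film clips guards against reader bias but not against this selection. Nor is it the familiar point that predictive values move with prevalence: here sensitivity itself shifts.

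**Working it through.** **The plan's own figure.** Sample size gives 50–75 events and 375–400 participants at about 20% intubation. 75 / 0.20 = 375, which reproduces the lower bound; 400 corresponds to 80 events. This serves the prediction model. No sample size is given for FLUS–PCR, so it is used here only to set N.

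**Inputs.** From the documents: N = 400, chi-square at 5%, positive-PCR route 100% PCR-positive. Assumed, because the documents give no values:

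- p = 0.30, PCR-positive share in the work-up route
- f_A = 0.40, FLUS-positive rate in the work-up route, the same in PCR-positives and PCR-negatives (FLUS uninformative)
- f_B = 0.40, 0.50, 0.60 or 0.80, FLUS-positive rate in the positive-PCR route
- s = 10%, 25%, 50% or 75%, share of the cohort from the positive-PCR route

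**Rejection rate of the pooled test.** Simulation with the uncorrected Pearson chi-square, 4,000 replicates per setting:

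| s | f_B = 0.40 | 0.50 | 0.60 | 0.80 |
|---|---|---|---|---|
| 10% | 5% | 7% | 19% | 55% |
| 25% | 5% | 19% | 56% | 99% |
| 50% | 5% | 32% | 84% | 100% |
| 75% | 5% | 29% | 79% | 100% |

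A repeat with 40,000 replicates agreed to within about 1.2 percentage points; the 7% cell came out at 8%. In work-up patients alone, rejection was about 5% throughout.

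**Other assumed rates.** N = 375, p = 0.30, 20,000 replicates, FLUS again uninformative in the work-up route:

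| FLUS-positive, work-up v positive-PCR route | s = 10% | 25% | 50% | 75% |
|---|---|---|---|---|
| 30% v 80% | 78% | about 100% | about 100% | about 100% |
| 50% v 80% | 33% | 88% | 99% | 99% |
| 30% v 50% | 20% | 58% | 84% | 79% |
| 50% v 60% | 8% | 18% | 30% | 28% |

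**Sensitivity against PCR.** Pooled sensitivity = [s·f_B + (1 − s)·p·f_A] / [s + (1 − s)·p]. With f_B = 0.80 and a work-up value of 40%:

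- s = 50%: (0.40 + 0.06) / (0.50 + 0.15) = 0.46 / 0.65 = 71%
- s = 25%: (0.20 + 0.09) / (0.25 + 0.225) = 0.29 / 0.475 = 61%
- s = 10%: (0.08 + 0.108) / (0.10 + 0.27) = 0.188 / 0.37 = 51%

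**Specificity.** All PCR-negatives are work-up patients, so specificity is 1 − 0.40 = 60% whether or not the inpatients are pooled.

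**The case against.** Several counter-arguments have force.

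- The documents never say that the test covers the whole cohort. The fault is an unstated population, not a wrong one stated. This stands, but with no restriction anywhere, an analyst following the plan would use everyone. Likewise, the line promising sensitivity and specificity sits in the prediction-model paragraph of Data analysis; that they would be computed against PCR is inferred from the hypothesis.
- The hypothesis concerns COVID-19 pneumonia, judged by PCR and radiograph, not infection alone. A PCR-positive patient without pneumonia should be FLUS-negative. This stands: 71% against 40% describes sensitivity for PCR positivity and does not measure bias for the pneumonia target.
- A reader might infer that the test measures only route of entry. That holds only if FLUS is uninformative among work-up patients. If FLUS does discriminate, real association and route difference are mixed, and the decision to reject may hardly change: with 60% v 40% FLUS-positive (assumed), 30% prevalence and N = 400 work-up patients, the test already rejects about 96% of the time. Sensitivity is still distorted when inpatients are added.
- A reader might also infer that false rejection is near certain. The documents do not support that, since the tables run from about 5% to 100% according to rates nobody has stated.
- The routes overlap. Some emergency-department patients will test positive and be admitted, which narrows the gap between routes. This reduces the bias but does not remove selection on PCR.
- The endpoint is secondary, and a significant chi-square alone could not establish high sensitivity and specificity. This limits the seriousness.

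**Conclusion.** The point holds as a defect in the definition of a secondary endpoint. Without a stated population, the default analysis adds patients selected on a positive PCR to one row of the table. The result then mixes diagnostic association with a difference between admitted and work-up patients, and sensitivity against PCR is overstated if admitted patients are more often FLUS-positive, as the Background suggests.

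The size depends wholly on assumed route shares, prevalence and FLUS rates. It ranges from no effect, when the routes do not differ, to near-certain rejection and a 31-point excess in sensitivity (71% − 40%) with half the cohort from the positive-PCR route and a wide gap. Sample size applies an intubation rate in admitted patients to the whole cohort, which hints at a substantial admitted share. It does not fix the route share, because work-up patients may be admitted too. The change should be made; the primary endpoint is not affected.

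**What to change.** In the Protocol's Data analysis section and in the SAP, state that the FLUS–PCR relationship, and sensitivity and specificity against PCR, are analysed in patients enrolled through the diagnostic work-up criterion, excluding those who entered only because of an already positive PCR. A patient who first enters for work-up stays in this set even if later found positive and admitted. This fits the existing exclusion of former participants, under which nobody enters twice.

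Record two items in the eCRF, if they are not already there: the entry route under that precedence rule, and whether the PCR result was known at enrolment. The second should not be a condition for inclusion in the analysis, since it could remove work-up patients whose negative result was already back. Report FLUS findings in the PCR-selected inpatients separately.

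The cost is two fields, a short statement in each document, and fewer PCR-positive patients. With N = 400 and half from each route, PCR-positives fall from 200 + 60 = 260 to 60. The 95% half-width for sensitivity becomes 1.96 × √(0.40 × 0.60 / 60) = 12 points, against 1.96 × √(0.71 × 0.29 / 260) = 6 points when pooled, but the narrower interval is centred on the inflated value. All PCR-negative work-up patients are kept, so specificity is unaffected. The intubation analyses do not change.

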Statistical analysis plan.

Study name: The use of Focused Lung Ultrasound in Patients Suspected of COVID-19.

8.April 2020

Descriptive data:		
Demographic	Age	Mean, sd
	Sex	% kvinder
	Weight	Mean, sd.
	Height	Mean, sd.
	Site	groupe
Baseline data	BT sys	Mean, sd.
	BT dia	Mean, sd.
	SAT	Mean, sd.
	Puls	Mean, sd.
	Respiratory Rate	Mean, sd.
	Oxygen, l/min	Mean, sd.
	ferritin	Mean, sd.
	Hbg	Mean, sd.
	Leukocytter	Mean, sd.
	Lymfocytter	Mean, sd.
	Mono	Mean, sd.
	Neutrofile	Mean, sd.
	Egfr	Mean, sd.
	Karbamid	Mean, sd.
	Kreatinin	Mean, sd.
	Natrum	Mean, sd.
	Kalium	Mean, sd.
	Ddimer	Mean, sd.
	Probnp	Mean, sd.
	Tnt	Mean, sd.
	Tni	Mean, sd.
	glucose hba1c	Mean, sd.
	ph	Mean, sd.
	pco2	Mean, sd.
	po2	Mean, sd.
	be	Mean, sd.
	bicarbonat	Mean, sd.
	lactat	Mean, sd.
	Rtg af thorax	Grupper
	CT thorax	Grupper
	Covid-19 pcr	Yes/No
Treatment data	Antibiotica	Yes/No
	Antiviral	Yes/No

	Biological	Yes/No	
	Anti thrombotic	Yes/No	
	Death during admission	Yes/No	
	Length of admission	kontinuert	
	Death at 30 days	Yes/No	
	Cause of death	Covid/ikke-covid	
	Treatment restrictions, ITA	Yes/No	
	Treatment restrictions, ventilator	Yes/No	
FLUS data.	L1	0-3	
	L2	0-3	
	L3	0-3	
	L4	0-3	
	L5	0-3	
	L6	0-3	
	L7	0-3	
	R1	0-3	
	R2	0-3	
	R3	0-3	
	R4	0-3	
	R5	0-3	
	R6	0-3	
	R7	0-3	
	Flus mean	0-3, sd	
Inter- intraobservatør agreement			
Limits of agreement. Bland altmann.		20% Flus film re-scored by 1.observatør	Weigthed kappa kap s1 s2, tab wgt(w)
		20% Flus film scored by 2.observatør	Weigthed kappa kap o1 o2, tab wgt(w)
Mean Flus score related to event:			
Covid death	Parametric distribution qq plot and histogram		
	Norm +	t-test.	ttest flusmed, by(covdod)
	Norm -	Wilcoxon	ranksum flusmed, by(covdod)
			by covdod, sort : summarize flusmed, d graph bar (Mean) flusmed, over(covdod)
ITA admission	Parametric distribution qq plot and histogram		
	Norm +	t-test.	ttest flusmed, by(ita_in)
	Norm -	Wilcoxon	by ita_in, sort : summarize flusmed, d ranksum flusmed, by(ita_in)

			graph bar (Mean) flusmed, over(ita_in)
Ventilator treatment	Parametric distribution qq plot and histogram		
	Norm +	t-test.	ttest flusmed, by(respirator_beh)
	Norm -	Wilcoxon	by respirator_beh, sort : summarize flusmed, d ranksum flusmed, by(respirator_beh) graph bar (Mean) flusmed, over(respirator_beh)
Prædiction of event			
Covid death	Univariat logistical regression	Variable: covdod flusmed	
	Multivariate logistical regression	Variable: covdod, Flusmed, alder, køn, sat, ilt (kategori?)	

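### The SAP's multivariable ventilator and ITA models leave out patients with a treatment restriction, while the unadjusted group comparisons of the same outcomes keep them, so results for one outcome come from different patients

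*Protocol*

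**What the plan says.** The protocol lists among the clinical data at admission "limitation to treatment i.e. not suited or willing to intensive care treatment and intubation". This is not among the exclusion criteria, so such patients are enrolled. The endpoint is "Primary endpoint: FLUS (binary: positive/negative pneumonia) related to intubation (yes/no", and the Data analysis section states "Binary endpoints, including primary endpoint, are analyzed using Chi-2 test". For the protocol's logistic model, "Dependent variable is intubation". Neither sentence carries a condition on treatment limitation. A secondary endpoint is "Relationship between FLUS and admission to intensive care (not intubation". The first aim is wider than intubation: "To study the ability of FLUS in COVID-19 to predictive respiratory failure".

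The SAP lists two restriction variables, one for ITA and one for ventilator, as yes/no descriptive items. Its group comparisons are written out as Stata code, for example "ttest flusmed, by(respirator_beh", with no if-clause. The ITA comparisons have the same form. Only the multivariable rows for ITA admission and ventilator treatment carry a condition, that the matching variable (`behandlingsloft_ita` or `behandlingsloft_resp`) equals zero. The section on building prediction models takes needing mechanical ventilation because of COVID-19 as the main outcome. It does not repeat the condition.

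**The concern.** Someone who reads the SAP results for ventilation would compare the unadjusted difference in mean FLUS score with the adjusted coefficient and put any change down to adjustment. As planned, the change also reflects the removal of restricted patients, and no text says why the populations differ.

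The second issue is what is being estimated. In an unfiltered analysis, a patient who may not be intubated and dies of respiratory failure is a non-event. That is correct for observed intubation, the protocol's primary endpoint. It is not correct for need for ventilation or for respiratory failure. COVID death is analysed without a filter, so these deaths appear there but in no ventilation result. If restriction is more or less common among FLUS-positive patients, the apparent association of FLUS with need for ventilation is shifted, and nothing planned would show it.

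**Working it through.** **1. The analyses side by side**

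| Analysis | Where | FLUS measure | Condition on restriction |
|---|---|---|---|
| Chi-square, intubation | Protocol, Data analysis | binary | none |
| Logistic model, intubation | Protocol, Data analysis | binary or ordinal | none |
| t-test and rank-sum, ventilator and ITA | SAP table, mean score by event | mean score | none |
| Univariable logistic, ventilator and ITA | SAP table, prediction of event | mean score | none shown; a merged table cell cannot be ruled out |
| Multivariable logistic, ventilator and ITA (score, age, sex, saturation) | SAP table, prediction of event | mean score | unrestricted patients only |
| Main prediction model (score, sex, age, comorbidity, oxygen) | SAP, Building Prediction Models | mean score | not mentioned |

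The variables of the main model differ from those of the filtered row, so the filter cannot simply be carried over to it.

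**2. The plan's own figure.** Five variables at 15 events give 75 events, and 75 / 0.20 = 375, the lower end of the protocol's 375-400. The upper end corresponds to 400 x 0.20 = 80 events. (The protocol names four variables; 50-75 events at 10-15 each implies five.)

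**3. Size of the effect.** The documents give neither the restriction share nor its relation to FLUS, so these are assumptions: need for ventilation 25% in FLUS-positive and 15% in FLUS-negative patients, 200 per group. The true odds ratio (OR) is (0.25/0.75) / (0.15/0.85) = 1.89.

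*Restriction unrelated to need within each FLUS group.* Observed risk = need x (1 - restriction share). The filtered OR is 1.89 by construction.

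| Restricted, FLUS-positive / FLUS-negative | Observed risks | Unfiltered OR |
|---|---|---|
| 10% / 10% | 0.225, 0.135 | 1.86 |
| 20% / 20% | 0.200, 0.120 | 1.83 |
| 30% / 20% | 0.175, 0.120 | 1.56 |
| 40% / 20% | 0.150, 0.120 | 1.29 |
| 20% / 30% | 0.200, 0.105 | 2.13 |
| 20% / 40% | 0.200, 0.090 | 2.53 |

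Of the 80 patients in need (50 + 30), those counted as not intubated number 50 x 0.20 + 30 x 0.20 = 16 at 20%/20%, 20 + 6 = 26 at 40%/20%, and 10 + 12 = 22 at 20%/40%. With 20% of FLUS-positives restricted, the unfiltered OR equals 1.89 when 22.1% of FLUS-negatives are restricted.

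*Restriction related to need.* Let a1, a0 be the restricted shares among patients in need and b1, b0 among those not in need (1 = FLUS-positive, 0 = FLUS-negative). Filtered OR = [0.25(1-a1) x 0.85(1-b0)] / [0.75(1-b1) x 0.15(1-a0)]. The unfiltered OR uses the risks 0.25(1-a1) and 0.15(1-a0).

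| Restriction pattern | Filtered OR | Unfiltered OR |
|---|---|---|
| 40% in FLUS-positives in need, 20% in all others | 1.42 | 1.29 |
| 40% in need, 20% not in need, both groups | 1.89 | 1.78 |
| 20% in FLUS-negatives not in need, 40% in all others | 2.52 | 1.78 |

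Against a truth of 1.89, filtering is closer in the first two rows and further away in the third.

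*A second set of assumptions:* 375 patients, 75 intubations, all among unrestricted patients, half of whom are FLUS-positive, OR 3.0 in them. With 20% restricted, the all-patient OR is 3.63, 2.81 or 1.88 if 25%, 50% or 90% of the restricted are FLUS-positive. Over 10-40% restricted and 25-90% FLUS-positive among them, it runs from 1.10 to 4.24.

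**4. Intubation or death by 30 days, all participants.** Assume 80% of restricted patients in need die. Composite risk = need x (1 - r + 0.8r), where r is the restriction share. The OR is 1.88 (20%/20%), 1.78 (40%/20%) and 1.97 (20%/40%), closer to 1.89 than intubation alone. If 5% of patients not in need also die, (1 - need) x 0.05 is added to each risk and the ORs fall to 1.68, 1.59 and 1.74. A version with COVID deaths only is therefore also needed.

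**5. Events.** If the 20% intubation rate applies to unrestricted patients only and 20% are restricted, there are 0.20 x 0.80 x 375 = 60 to 0.20 x 0.80 x 400 = 64 events. The SAP's rule requires 15 x 4 = 60 for the filtered row. The protocol divides the data set in two; an equal split leaves about 30-32 for development. If the 20% applies to everyone, 75-80 events become about 37-40. Either way the rule is not met in the development half.

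**The case against.** The strongest counter-argument is that the size rests on assumed imbalance. With equal restriction the OR moves only from 1.89 to 1.83 at 20%/20%. This stands, and it limits severity.

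The populations are also not wholly undefined. The filter is explicit, and a command without a condition uses everyone with data. What is missing is a reason for the difference and any breakdown by FLUS result. The planned descriptive items (both restrictions, deaths, cause of death) do not supply that breakdown.

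The protocol's chi-square test uses binary FLUS and the SAP the mean score, so those two results would differ anyway. The direct inconsistency is therefore inside the SAP. The univariable rows should not be counted as evidence, because the table may have had a merged cell. The written-out t-test and rank-sum commands do not share that doubt.

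Two stronger readings are tempting. A reader might infer that the primary chi-square test is wrong. It is not: it correctly addresses observed intubation, which is the stated endpoint. A reader might also infer that extending the filter everywhere gives the right answer. The third pattern in the restriction-by-need table shows that it can do worse. Filtering also has a practical hazard. Restriction is listed with admission data, yet patients seen only in COVID clinics are enrolled. If the field is blank for them, Stata's `==0` drops them. The SAP gives no time point for its restriction variables, so they may not be the admission record.

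**Conclusion.** The inconsistency is real: for ventilation and for ITA admission, the SAP's unadjusted group comparisons and its multivariable models use different patients without explanation, and the population of the main prediction model is not settled. Its effect is small if restriction is similar by FLUS result and can be material if it is not (1.29 to 2.53 against 1.89 in the first illustration). All these figures depend on assumed shares, and the planned output would not show which case applies. The documents do not support preferring one population throughout. The reduced sample of the filtered row, and its 60-64 events under the stated assumption, belong to the current plan and are not a cost of the change. Severity lies between minor and should-fix.

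**What to change.** 1. For ventilation and ITA admission, run the group comparisons, univariable models and multivariable models, including the main prediction model, in the same population. Report each both in unrestricted patients and in all participants. State whether the SAP restriction variables are the restriction recorded at admission, and count and report blank values so that `==0` does not remove patients unnoticed.
2. Keep the primary chi-square test in all participants, label it as observed intubation, and repeat it in unrestricted patients.
3. Add a sensitivity analysis in all participants of intubation or death by 30 days, and repeat it counting COVID deaths only. The protocol already collects "In hospital survival, 14- and 30-days survival", and the SAP lists cause of death.
4. Report the number restricted, and deaths among them, by FLUS result.

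The cost is SAP wording and a few lines of code, with no new data items. The downsides are somewhat more analysis and filtered results that apply to unrestricted patients only (300-320 of 375-400 if 20% are restricted).

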ITA admission	Univariat logistiscal regression	Variable: ita_in flusmed	
	Multivariate logistical regression	Variable: ita_in, Flusmed, alder, køn, sat	, if behandlingsloft_ita ==0
Ventilator treatment	Univariat logistical regression	Variable: respirator_beh flusmed	
	Multivariate logistical regression	Variable: respirator_beh Flusmed, alder, køn, sat	, if behandlingsloft_resp ==0

Continuous variables are assessed for parametric distribution with quartile-quartile plots. Medians, interquartile ranges or means and standard deviations and ranges are reported according to parametric distribution. Students' t-test or Mann-Whitney U test is used as it was considered appropriate to evaluate differences between groups. The statistical significance is set to 5%. All data are handled in Excel (Microsoft) and REDCap (hosted at Aarhus University). All analyses are performed using Stata 14.2 (StataCorp, USA).

Building Prediction Models

Prediction models are based on multivariable logistic regression and preselected variables. The variables are sex, age, relevant comorbidity, oxygen administration and the mean-FLUS score. The selection of these variables is based on published data and clinical experience available to the study group during the study design stage. Explanatory variables are examined to decide cut-points, scales or the need for transformation. Variables are limited and prioritized to avoid overfitting or underfitting, respecting the study population size. Every included variable require at least 15 events.

The dependent variable is the primary outcome of interest: the COVID-19-related need for mechanical ventilation in the main analysis. Secondary outcomes are analyzed using the same logistic regression model, except for the outcome on high-flow oxygen treatment. The explanatory variable on oxygen administration is considered closely related to the outcome and is thus excluded from this analysis.

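### The protocol and the same-date SAP give different tests for non-normal continuous data, and the protocol's log rule cannot be computed for a FLUS score of 0

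*Protocol*

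**What the plan says.** **Protocol, Data analysis.** The rule for continuous variables is a check of the distribution, followed by a Student's "T-test on logarithmic transformed data in case of non-parametric distribution". No rank test, offset or treatment of zeros is given. Binary endpoints, the primary endpoint among them, go to a chi-squared test.

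**Protocol, Variables and Endpoints.** The scoring table gives a normal FLUS the value 0 on a scale from 0 to 3. One secondary endpoint is "Scores of FLUS findings in different zones". In the prediction model the ultrasound term is "FLUS result (Binary or ordinal"; a mean FLUS score is not defined anywhere in the protocol.

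**SAP, table.** Mean FLUS, range 0-3, is a variable here. Under "Mean Flus score related to event" it is compared between patients with and without COVID death, intensive care admission and ventilator treatment. If the distribution looks normal, a t-test is used; if not, a Wilcoxon test on the score as it stands, down to the Stata command (for example "ranksum flusmed, by(covdod" and "ranksum flusmed, by(respirator_beh", each followed by a closing bracket).

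**SAP, text on continuous variables.** The choice is between a t-test and a rank test: "Mann-Whitney U test is used as it was considered appropriate to evaluate differences between groups". No log transformation appears in this rule.

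Both documents are dated 8 April 2020, and neither contains a statement of precedence.

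**The concern.** Two documents of the same date give different instructions for the same situation: a continuous variable, two groups, a distribution judged not normal. The two tests also answer different questions. A t-test on logs compares geometric means among patients with a positive value; a rank-sum test compares the ordering of all patients. An analyst could follow either and call it prespecified.

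For FLUS the difference goes beyond taste. The log rule has no value for a score of 0, which is the score of a normal scan. A bounded 0-3 score, in a cohort that includes people seen only for diagnostic work-up, may well have a cluster at 0 and fail a normality check, and that is the condition that triggers the rule. Patients lost this way would be selected by the exposure itself: only the lowest scores go. If all-normal scans are commoner in patients who are not ventilated, as the study's hypothesis implies, their removal would hide part of the difference being tested.

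**Working it through.** **1. The two rules side by side.**

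| | Protocol | SAP |
|---|---|---|
| Data judged normal | t-test | t-test |
| Data judged not normal | t-test on logs | Wilcoxon / Mann-Whitney, untransformed |
| Score of 0 | no value, no rule given | lowest rank, kept |
| Date | 8 April 2020 | 8 April 2020 |

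**2. Who would be lost under the log rule.** The log of 0 is undefined. With 14 zones scanned, the smallest non-zero mean is 1/14 = 0.071, and its natural log is -2.64, which is computable. So in a mean-score comparison only patients with every scanned zone normal are lost; one abnormal zone is enough to stay in.

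**3. How many.** No figure in the plan can be reproduced here, because the share of all-normal scans is not stated. The nearest figure, in the Background, is that over 80% of admitted patients had abnormal chest radiographs. That concerns radiographs, not FLUS, and only admitted patients.

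The range below therefore rests on assumption. Take the protocol's upper event target and rate: 75/0.20 = 375 patients, of whom 75 are intubated and 300 are not. Let z0 and z1 be the assumed shares of all-normal scans in non-intubated and intubated patients. Expected loss = 300 × z0 + 75 × z1.

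| z0 / z1 (assumed) | Calculation | Lost | Share of 375 |
|---|---|---|---|
| 10% / 0% | 30 + 0 | 30 | 8% |
| 20% / 5% | 60 + 3.75 | about 64 | 17% |
| 30% / 5% | 90 + 3.75 | about 94 | 25% |
| 50% / 10% | 150 + 7.5 | about 157 | 42% |

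Under the SAP's rank-sum test the loss is 0 in every row.

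**4. Would an offset settle it?** Only if its size were fixed beforehand. In an illustrative simulation of the first row (3000 runs, two-sided 5%, a small assumed shift among the non-zero scores), power was 64% with log(x + 1) and 95% with log(x + 0.01). With the zeros lost it was 13%; with the rank-sum test in all patients, 57%. These values depend on the assumed distributions. They show only that the result is sensitive to a constant that the protocol does not name.

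**5. What the log rule does not reach.** The primary endpoint is a two-by-two table tested by chi-squared. The rule concerns a t-test, so the logistic models in both documents are outside it.

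**The case against.** The strongest reply is that the log rule and a continuous FLUS score never meet in one document. The protocol treats FLUS as binary or ordinal and applies the log rule only to continuous data. Mean FLUS exists only in the SAP, and the SAP tests it untransformed with a rank-sum command for all three events. This stands, and it limits the point. A reader might infer that the plan drops patients with normal scans. The documents do not say so: the loss arises only if the score is treated as continuous, is judged not normal, and is analysed by the protocol's rule instead of the SAP's.

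Three further inferences are tempting and are not supported:

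- **Zone scores.** The protocol lists them without a comparison group, and the SAP lists them as descriptive data. A log-based test of them is not actually planned.
- **Oxygen flow and base excess.** These can be zero, or for base excess negative, but they appear only in the SAP's descriptive table, and the SAP's rule for group differences contains no log transform.
- **Out-patient management.** The Background ties this idea to the absence of pneumonic findings, which is the binary reading. It does not rest on the comparison of mean scores.

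A log transform is also a legitimate choice for strictly positive skewed variables, so the rule need not be removed altogether. What the reply does not remove is the contradiction. The SAP is more specific and probably shows the intended method, but without a precedence statement the protocol's sentence remains a valid instruction.

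**Conclusion.** The point holds as a contradiction between two documents of the same date, in which one of the two rules cannot be computed on the study's own score. Following the protocol's rule for mean FLUS would exclude patients with all-normal scans, a loss tied to the exposure; following the SAP's would exclude nobody. The effect is confined to the group comparisons of mean FLUS. The number at risk cannot be derived from the documents, and the 30 to 157 of 375 shown above is no more than arithmetic on assumed shares. It should be corrected before analysis, but it does not threaten the primary endpoint.

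**What to change.** In the protocol's Data analysis section, replace the log-transform rule, for FLUS scores and for any other variable that can be zero or negative, with the SAP's Wilcoxon rank-sum test on untransformed values in all patients. Add one sentence saying that the SAP governs where the two documents differ. The log transform may remain an option for strictly positive skewed variables. If a log analysis of FLUS is wanted after all, its offset must be fixed in advance.

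The cost is about two sentences in the protocol. No data collection or sample size changes, and the SAP's test commands stay as they are.
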